- (2) **Control Conditions Hypothesis:** We hypothesize significant differences in signal intensity across the three different epoch conditions—TM, passive-attending and mental-counting. Specifically, de-excitation will be maximum for TM, then passive-attending, and lastly, mental-counting.

Aim 2: Maximum De-excitation Meditation Substate. We predict that event-related (er-fMRI) and state-related (sr-fMRI) analytic procedures will yield distinct spatial and temporal patterns of BOLD intensity that characterize the maximum de-excitation substate associated with spontaneous breath-quiescent periods (SBQ, breath period > 10 sec). We will test five hypotheses in this experiment.

- (3) **IBH-Blood Gas Hypothesis:** Using event-related-fMRI, we hypothesize moderate changes in blood gas changes will be detected during Intentional Breath-Holding (IBH), and blood gas levels will be significantly correlated with changes in BOLD signal intensity, consistent with published findings.
- (4) **SBQ-Blood Gas Hypothesis:** Using event-related-fMRI, we hypothesize small changes in blood gas changes will be detected during Spontaneous Breath Quiescence (SBQ), and blood gas levels will not be significantly correlated with changes in BOLD signal intensity.
- (5) **SBQ-IBH Hypothesis:** Using event-related-fMRI, we hypothesize that specific spatiotemporal patterns of BOLD signal will be associated with onset of SBQ, and will differ from IBH control periods in terms of reduced BOLD signal of the anterior cingulate cortex and brainstem during SBQ.
- (6) **SBQ-Controls Hypothesis:** Using state-related-fMRI, we hypothesize that BOLD signal intensity patterns during SBQ periods will differ from two control conditions—IBH periods, and eyes-closed periods (as defined in Aim 1, either passive-attending or mental-counting).
- (7) **SBQ-Non-SBQ Hypothesis:** Using state-related-fMRI, we hypothesize that BOLD signal intensity patterns during SBQ periods will differ from the scans during non-SBQ periods during meditation.

B. BACKGROUND AND SIGNIFICANCE

B.1. Need for Basic Neuroscience Research on Mechanisms of CAM Modalities.

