Prior to fMRI runs, subjects practiced meditating at home in a supine position (in contrast to normal upright sitting position) with a audio recording of fMRI noise. Subjects came to the M.U.M. lab and did a 'dry'

run in a fMRI machine mockup with audiotape to simulate the actual run experience (noise, claustrophobia, etc.). Physiological markers were recorded and the signaling paradigm between the subject and the experimenter was tested (use of audio vs. light beam signals). Subjects filled out consent forms at M.U.M. and UI before testing. Following selection procedures, subjects went to the UI MR Center for testing.

C.2.3. Acquisition Protocol.

Subjects were reminded again of the nature of the experiment and signaling protocols. Following setup and positioning in the scanner, we acquired standard anatomic scans lasting about 40 minutes before experimental scans. The anatomic scans included: (1) a T2-weighted sagittal localizer using a fast spin echo sequence (TE/TR 100/4500; 24 5mm slices; 2mm space; 256X224, NEX2 1:30); and (2) a volumetric scan (3D RF-spoiled gradient echo sequence with TE/TR 7/26 ms; 256X192 matrix). Experimental scans included (1) a 2D T1-weighted scan of the slices to be acquired in the fMRI study (2D RF-spoiled gradient echo sequence with TE/TR 7/26ms), and (2) an 8-shot EPI sequence of the slices to be acquired (TE/TR 40/3000 ms). The 8-shot EPI sequence and T1-weighted slices are used to align the fMRI data with the volume scan. For fMRI studies, we used the EPI sequence with 128 by 128 data acquisition matrix, TE of 40 msec, TR of 3 sec, FOV 24 cm, slice thickness of 5 mm. Since fMRI was conducted on a single slab (software limitation of the 1.5T GE scanner system), we initially chose a slab (5 slices, 118 degree angle) that traversed regions of greatest interest (see figure 1A): progressing from anterior/superior to posterior/inferior, the regions of interest included the prefrontal cortex (anterior polar, dorsolateral, ventromedial and rostral anterior cingulate), the basal forebrain and hypothalamus, the thalamus, the mesencephalic brainstem and the cerebellum. We were aware of the possibility of tissue ghosting.

[figure not shown]

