We will acquire standard anatomic scans during an initial 40 minutes period before experimental scans. The anatomic scans include: (1) a 3 plane localizer using a fast gradient echo sequence (TE/TR 1.7/32.1 ms); (2) a volumetric scan (3D Fast RF-spoiled gradient echo sequence with TE/TR 3.7/9.1 ms); (3) a 2D T1-weighted FLAIR scan of the slices to be acquired in the fMRI study (2D fast spin echo sequence with TE/TR 7/26ms), and; (4) an 8-shot EPI sequence of the slices to be acquired (TI/TE/TR 860/5.9/1977 ms). The EPI sequence and T1-weighted slices are used to align the fMRI data with the volume scan. For fMRI studies, we currently use the product EPI sequence with 64 by 64 data acquisition matrix, TE of 30 ms, TR of 2.2 sec, FOV 24 cm, slice thickness of 5 mm. 19 slices are acquired in an interleaved fashion (odd first, then even) for the entire time the paradigm is being performed. Following these standard MR scans subjects will perform a simple motor task cycling run (alternating 45 sec episodes of rest and hand-squeezing). This run represents a positive control for the cycling acquisition and analysis in every run.

D.2.2. Data analysis.

The HFH fMRI facility possesses real time fMRI acquisition and analysis software. [name] [181-183] has developed software for er-fMRI analysis [see also 168, 172, 173, 178]. A data analysis system, similar to the system at MSU/HFH, will be installed at M.U.M. This system will complement the AFNI system already running. The HFH software acquires fMRI images and other physiological data (pulse oximetry, respiration, electrocardiogram) on the same computer, allowing a synchronized time-stamp on all data sets. Each channel of acquired data contains a corresponding data file and a timing file. The time series from these other physiological variables will be used as real-time covariables in multiple linear regression, thereby statistically controlling for the contributions of breath rate and CO₂ to the overall BOLD effect.

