The BOLD signal and physiological measures will be collected during four runs of 12 minutes duration each. Each 12 min run comprises three periods: 5 min uninterrupted meditation, 5 min structured breath-holding, and 2 mins non-task, eyes-closed (EC) control. The meditation period are free running with no interruptions from experimenters. During the meditation period we expect 3-5 SBQ periods. The breath-holding periods are structured by duplicating the previous SBQ pattern by voice command from experimenter, the onset and offset of IBH corresponding to SBQs time frame for each subject. The non-task control period will be determined from the outcome of experiment 1 (Aim 1), and either be passive-attending or mental-counting. The physiological measures will include respiration and transcutaneous CO₂ measurements. Four runs will take 48 minutes, or about 1 hr due to 30 rest periods between conditions. Therefore, each fMRI session will last about 90 minutes per subject.

D.6.4. Event-related fMRI analysis (Hypotheses 1-3).

Er-fMRI methodologies will be used to probe brain mechanisms during the onset of two conditions, during SBQ and IBH periods. The scans will be aligned relative to the onset of either SBQ or IBH during the four runs to permit signal averaging: 4 images before (12 secs) and 4 images after onset (12 secs). A TM meditator, selected in our screening protocol, may exhibit 25-30 spontaneous breath-quiet periods in a 30-min TM session [9, 20-22]. We estimate 12-20 periods will occur in our four meditation periods.

Images from individual runs will first be normalized to correct for the range of intra- and inter-subject signal intensity and temporal drift [171]. Specifically, normalization will involve: (1) scaling of signal intensity to a fixed value of 1000; (2) linear slope removal in a voxel-by-voxel basis; (3) spatial filtering with a one-voxel radius Hanning filter, and; (4) removal of the mean signal intensity on a voxel-by-voxel basis. The normalized fMRI images will then be aligned relative to the onset either SBQ or IBH periods. These images will be averaged within each subject. The mean image for each subject will be transformed into stereotaxic atlas space [208] using the highest point of the mid-sagittal plane and the anterior and posterior commissures. The atlas-transformed matrices will then be averaged across subjects.

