Statistical parameter maps will be constructed using sets of pre-constructed hemodynamic curves. Cohen's hemodynamic model, often used in fMRI experimental analysis, was derived from stimulation of the visual cortex [170]. Hence, there is no reason to suspect it is the best response function to apply to this task (meditation) or to other brain areas (subcortical nuclei). Therefore, new response models will be constructed by systematically varying, initially, the onset delay (lags) of Cohen's standard hemodynamic response model. Other parameters besides onset could also be varied, e.g., shape of curve. Sequential application of each model will display the inherent temporal and spatial dynamics of the hemodynamic response to the onset of the spontaneous breath-quiet substate. Each model will generate a different map of the brain dynamics. For example, short versus mid or long lags could be reasonably expected to produce different anatomical patterns [171]. On the other hand, the brain pattern may remain similar, but the signal intensity of each brain area may vary. Models derived from both conditions can be compared to determine statistical significance of the two brain states. Specifically, we will use MANOVA to compare onset, latency and peak signal intensity for different ROIs for the two conditions. We expect, in general, that the statistical parameter maps for intentional breath-holding will depict a diffuse, non-localized distribution of activation in contrast to localized patterns of activation during spontaneous breath-quiet. Hypothesis 1 & 2 will use a correlational analysis to test association between er-fMRI BOLD signal intensity and blood gas levels.

D.6.4.1 Blood Gases and IBH. O₂ and CO₂ levels will be correlated with er-fMRI BOLD signal intensity during the 6 scans (18 s) preceding and the 4 scans (12 s) following the onset of IBH. Data will be analyzed with a Pearson correlation to help distinguish blood gas-dependent vs. neural-dependent BOLD changes.

- We expect significant correlations between CO₂, but not O₂, with BOLD signal during IBH.

D.6.4.2. Blood Gases and SBQ. O₂ and CO₂ levels will be correlated with er-fMRI BOLD signal intensity during the 6 scans (18 s) preceding and the 4 scans (12 s) following the onset of spontaneous breath-quiet. Data will be analyzed with a Pearson correlation help distinguish blood gas-dependent versus neural-dependent BOLD changes.

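### The event-related windows in D.6.4 equate images with seconds at 3.0 s per image, but the study's stated scan interval is 2.2 s, so image counts and durations cannot both hold

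*Protocol*

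**What the plan says.** **Scan interval.** D.2.1, under the standard acquisition and analysis protocol for this study, states: "we currently use the product EPI sequence with 64 by 64 data acquisition matrix, TE of 30 ms, TR of 2.2 sec". No other TR is given for Experiment 2. The preliminary study, run earlier at a different imaging centre, is described in C.2.3: "we used the EPI sequence with 128 by 128 data acquisition matrix, TE of 40 msec, TR of 3 sec".

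**Event-related windows.** For signal averaging around the onset of spontaneous breath quiescence (SBQ) or intentional breath-holding (IBH), D.6.4 takes "4 images before (12 secs) and 4 images after onset (12 secs"). For the blood-gas correlations, D.6.4.1 works "during the 6 scans (18 s) preceding and the 4 scans (12 s) following the onset of IBH", and D.6.4.2 uses "the 6 scans (18 s) preceding and the 4 scans (12 s) following the onset of spontaneous breath-quiet".

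**The events.** Aim 2 concerns "spontaneous breath-quiescent periods (SBQ, breath period > 10 sec"), and D.1 and D.6.2 give durations of 10 to 40 s. D.6.3 times each subject's breath-holds to copy that subject's own SBQ pattern.

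**Use of the windows.** D.6.4 serves the three event-related hypotheses, numbered 3, 4 and 5 in the Specific Aims (1-3 in the heading of D.6.4). It plans to vary the lag of the response model and to compare the timing and peak of the response between SBQ and IBH.

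**The concern.** Each window is specified twice, as a number of images and as a number of seconds, and the two agree only at a scan interval that the study does not state for itself. An analyst who follows the counts and one who follows the seconds would extract different data from the same run. Neither would be departing from the text, and neither would be fully complying with it.

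The choice affects the inputs to Hypotheses 3, 4 and 5. If the counts are followed at 2.2 s, the post-onset stretch is shorter than the authors appear to have intended. A late peak or a long-lag response then has less room to appear, and less of any CO₂ change that builds up over the pause is captured. Hypothesis 4 is the most exposed because it predicts no significant blood-gas correlation for SBQ. A truncated window could contribute to that result for a reason unrelated to physiology. If the discrepancy is resolved only once the data are in view, the choice of window also becomes a matter of analyst discretion.

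**Working it through.** **Inputs**
- TR for this study: 2.2 s (D.2.1).
- TR for the preliminary study: 3 s (C.2.3).
- Averaging window: 4 images = 12 s on each side of onset (D.6.4).
- Correlation window: 6 scans = 18 s before and 4 scans = 12 s after onset (D.6.4.1 for IBH, D.6.4.2 for SBQ).
- SBQ duration: 10 to 40 s (D.1, D.6.2).

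**Step 1: reproduce the plan's figures.** Implied interval = seconds ÷ images. 12 ÷ 4 = 3.0 s and 18 ÷ 6 = 3.0 s. At TR 3 s both reproduce exactly: 4 × 3.0 = 12 s and 6 × 3.0 = 18 s.

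**Step 2: apply the study's TR, letting the image counts govern.** Duration = images × 2.2 s.

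| Window | Images | Stated | At 2.2 s |
|---|---|---|---|
| Averaging, each side of onset | 4 | 12 s | 8.8 s |
| Averaging, total | 8 | 24 s | 17.6 s |
| Correlation, before onset | 6 | 18 s | 13.2 s |
| Correlation, after onset | 4 | 12 s | 8.8 s |
| Correlation, total | 10 | 30 s | 22 s |

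The shortfall is the same in every row: 1 − 2.2/3.0 = 0.267, or 27%.

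**Step 3: apply the study's TR, letting the seconds govern.** Images = seconds ÷ 2.2.
- 12 ÷ 2.2 = 5.45. Five images reach 11.0 s and six reach 13.2 s.
- 18 ÷ 2.2 = 8.18. Eight images reach 17.6 s and nine reach 19.8 s.

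Neither is a whole number, and neither matches the stated counts of 4 and 6.

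**Step 4: share of a breath pause covered after onset.** Share = window ÷ pause length, capped at 100%.

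| Pause length | 8.8-s window | 12-s window |
|---|---|---|
| 10 s | 88% | 100% |
| 20 s | 44% | 60% |
| 40 s | 22% | 30% |

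The mismatch therefore costs coverage at every pause length. Even the stated 12 s covers only part of the longer pauses.

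**The case against.** **Which figure governs.** The 8.8 s applies only if the image count governs. If the seconds govern, the window is 12 s and the count is what is wrong. D.2.1 also speaks of the sequence in current use, which leaves room for a later change of TR. Both points stand and make the 27% conditional. They do not remove the contradiction: no later TR is stated, a 3-s reading conflicts with D.2.1, and a 2.2-s reading conflicts with D.6.4.

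**Whether the images belong to SBQ.** Because 8.8 s is below the 10-s criterion, a reader might infer that the window closes before the event qualifies as SBQ. The documents do not support that. Scans are recorded continuously and then aligned to the onset of an identified pause, so the first 8.8 s lies inside a pause that goes on to qualify. The criterion classifies events; it does not set a minimum analysis window.

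**Whether the window must span the event.** A reader might add an assumed haemodynamic lag of 4-6 s to the 10-40 s pause, obtain roughly 7 to 21 images ((10 + 4) ÷ 2.2 = 6.4; (40 + 6) ÷ 2.2 = 20.9), and call four far too few. But D.6.4 is an analysis of onset. The pause itself is handled by the state-related analysis in D.6.5, which bins scans before and during each condition. Nor is it shown that the peak is lost: the assumed lag fits inside 8.8 s, and D.6.2.1 describes breath-hold signal changes as rapid.

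**Bias.** A reader might infer a general bias towards small effects. The same windows apply to SBQ and to IBH timed to match it, so truncation does not obviously favour either side of Hypothesis 5. It would work against Hypothesis 3, which predicts a correlation for IBH. Only the null prediction of Hypothesis 4 could plausibly be helped.

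**Four versus six pre-onset images.** This is not necessarily a contradiction. One window serves signal averaging and the other the Pearson correlations; the protocol simply does not say whether the difference is intended.

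**Conclusion.** The inconsistency is established from the protocol's own figures. D.6.4, D.6.4.1 and D.6.4.2 all assume 3.0 s per image, while D.2.1 sets 2.2 s. Carry-over from the preliminary study would explain it, but the document does not say so.

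If the counts govern, the windows are 8.8 s and 13.2 s, 27% shorter than stated. If the seconds govern, about 5.5 and 8.2 images are needed in place of 4 and 6. Either way the specification behind Hypotheses 3 to 5 must be reconciled before it can be run. This rests on one assumption: that the TR in D.2.1 is the one used in Experiment 2.

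The consequence is limited and conditional. If the counts govern, the post-onset images sample only the early part of most pauses, leaving less room for latency, peak and long-lag estimates and possibly favouring the null in Hypothesis 4. How much signal would be lost cannot be determined from the document. No data are lost, and the state-related hypotheses in D.6.5 do not use these windows.

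**What to change.** Before analysis:

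1. Define each event-related window in seconds and convert it at the TR actually used. At 2.2 s, at least 6 images are needed to cover 12 s. For 18 s, 8 images fall just short (17.6 s) and 9 cover it in full (19.8 s). State the rounding rule.
2. Correct the image counts in D.6.4, D.6.4.1 and D.6.4.2 together. If the TR for Experiment 2 is to differ from D.2.1, state it there.
3. Say whether the 4-image and 6-scan pre-onset windows are meant to differ, and why. A single common window is not required.

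A longer post-onset window is optional. If one is wanted for the latency and peak estimates, limit it to each event's own offset plus a stated haemodynamic lag. A fixed long window, say 30 s, would bring about 20 s of post-pause scans into a 10-s SBQ (30 − 10 = 20), which is the substate mixing that B.2.4.2 and C.2.6.3 caution against.

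The cost is a change of text and a revised image count. Scanning within the meditation period is continuous, so no additional acquisition is needed.

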- We expect minor blood gas changes and hence, few significant correlations between CO₂, with BOLD signal during spontaneous breath-quietness.

D.6.4.3. Neuroimages during SBQ and IBH. Er-fMRI will be compared between IBH and SBQ periods, using a repeated measures MANOVA.

- We expect main effects for brain areas. Animal hypercapnia [209] and human breath-holding [157, 203, 210, 211] studies indicate that hypercapnic conditions are associated with global increases in most cortical and subcortical grey matter blood flow. Thus, we expect region-independent, nonspecific activation in all areas during IBH. In contrast, we expect region-dependent, specific activation or deactivation of BOLD signal intensity during SBQ.
- We expect main effects for the repeated measures, indicating significant differences in signal intensity across time.
- We expect no significant interactions.

D.6.5. State-related fMRI analysis (Hypotheses 4-5).

Sr-fMRI methodologies will be used to probe brain mechanisms during SBQ, IBH, and control periods. In the previous three analyses, we identified brain areas that displayed significant time-locked relation to the onset of both IBH and SBQ. A complementary approach to identification of brainstate changes is the use of state-related methodology. This method divides the time-series into condition-specific bins for comparison. Scans collected in Expt. 2 will be categorized into six bins: before and during either IBH, SBQ or equal-length periods during eyes-close (EC) control. Scans assigned to each bin will be compared by multiple linear regression, correcting for differences in blood gas levels across the three conditions.

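### D.6.4.3 looks for regional activation in a brain-area main effect which, once each voxel's mean has been removed, does not measure the response and can fall to zero or below

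*Protocol*

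**What the plan says.** Protocol D.6.4 sets the order of processing. "Images from individual runs will first be normalized to correct for the range of intra- and inter-subject signal intensity and temporal drift"; the four steps are scaling, linear slope removal, spatial filtering and "removal of the mean signal intensity on a voxel-by-voxel basis". Alignment comes afterwards: "The normalized fMRI images will then be aligned relative to the onset either SBQ or IBH periods". The aligned window has four images before and four after onset. No step re-references an event to its own pre-onset images.

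D.6.4.3 compares IBH with SBQ by repeated measures MANOVA. Its first expectation reads "We expect main effects for brain areas", and under it the plan states that "we expect region-dependent, specific activation or deactivation of BOLD signal intensity during SBQ", while IBH should activate all areas alike. It also expects a main effect of the repeated measure, described as change in signal over time, and no significant interactions.

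D.6.3 gives the run: "Each 12 min run comprises three periods: 5 min uninterrupted meditation, 5 min structured breath-holding, and 2 mins non-task, eyes-closed (EC) control". It adds "During the meditation period we expect 3-5 SBQ periods", and the breath-holds copy them, "the onset and offset of IBH corresponding to SBQs time frame for each subject". D.6.2 puts SBQ at 10 to 40 s.

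**The concern.** Once a voxel's mean over the run is subtracted, its zero point is no longer rest. It is an average that already contains the responses to SBQ and IBH. A brain-area main effect then averages the aligned signal over images before and after onset and over both conditions. What is left for an area depends on how much of the run is spent in events, as well as on how strongly the area responds.

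The stake is the regional reading. If the multiplier is near zero, real differences between areas vanish from this effect. If it is negative, the most activated area has the lowest mean, and any follow-up comparison of area means would rank the areas in reverse. Areas with different response lags can also receive different multipliers for the same response.

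**Working it through.** The plan states no figure for this point, so there is none to reproduce.

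**Inputs**
- Run length 300 + 300 + 120 = 720 s (D.6.3).
- n = 3 to 5 SBQ per run, with the same number and timing of IBH (D.6.3).
- Duration d = 10 to 40 s (D.6.2).
- Window: 4 + 4 images, given as 12 s + 12 s (D.6.4). D.2.1 gives a TR of 2.2 s, which makes 4 images 8.8 s, so both are run.
- Hemodynamic delay: no value is given in the protocol. Assumed 0 or 5 s.

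**Formula.** Let an area rise by A during every event. After subtraction of the run mean its signal is A x (response on or off) - fA. Averaged over the window this is (w - f)A, with
- f = 2 x n x d / 720, the raised share of the run;
- w = the raised share of the window.

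**Values of f**
- 3 x 10 s: 60/720 = 0.083
- 4 x 25 s: 200/720 = 0.278
- 5 x 40 s: 400/720 = 0.556

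**Values of w**
- No delay, 12-s windows: 10/24 = 0.417 for a 10-s event; 12/24 = 0.5 for events of 12 s or more.
- 5-s delay, 12-s windows: 7/24 = 0.292.
- 5-s delay, 8.8-s windows: 3.8/17.6 = 0.216.

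**Area average, (w - f)A**

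| Events per condition | No delay, 12 s | 5-s delay, 12 s | 5-s delay, TR 2.2 s |
|---|---|---|---|
| 3 x 10 s | +0.33A | +0.21A | +0.13A |
| 4 x 25 s | +0.22A | +0.01A | -0.06A |
| 5 x 40 s | -0.06A | -0.26A | -0.34A |

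**Different lags.** D.6.4 expects lags to differ by anatomy. At 4 x 25 s with 12-s windows, a 3-s lag gives 9/24 - 0.278 = +0.10A and a 6-s lag gives 6/24 - 0.278 = -0.03A. Two areas with equal A receive opposite signs.

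**Simulation.** The formula ignores slope removal and the shape of the response. The run was therefore simulated with the first three scans dropped, slope and mean removed, and a gamma-shaped response peaking near 4.75 s.
- 3 s per image: +0.21A (3 x 10 s), +0.07A (4 x 25 s), -0.11A (4 x 40 s).
- TR 2.2 s, 4 x 25 s: -0.04A.
- SBQ-only response, 3 s per image: -0.01A at 4 x 25 s and -0.10A at 4 x 40 s. The formula alone would halve the values and keep their sign. Slope removal shifts them further.

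**Other averaging periods.** D.6.4 does not name the period over which the mean is taken.
- Over the 5-min period, f = nd/300. At 4 x 25 s this is 100/300 = 0.333, which with the 5-s delay and 12-s windows gives 0.292 - 0.333 = -0.04A.
- Over the event window, the area average is exactly zero.

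**The case against.** The strongest reply is that the MANOVA's variate is not fixed as the time-point signal. D.6.4 itself names onset, latency and peak intensity as quantities to compare by MANOVA, and D.2.3 carries Z-statistics into parametric analyses. Subtracting a constant per voxel leaves onset, latency and a regression Z-statistic (fitted with an intercept) unchanged. It lowers peak intensity, but the peak stayed positive in every simulated case. This stands, and the point is conditional on the variate. The time-point reading remains the natural one for D.6.4.3, because its repeated measure is signal over time.

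The hypothesis behind D.6.4.3 is the SBQ-IBH difference, and the removed mean cancels from that contrast. This also stands. A reader might infer that the SBQ-IBH test is invalidated, or that voxel-wise mean removal is an error in itself. The documents support neither: the step removes static intensity differences between areas, and the problem arises only when it is paired with an area main effect.

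An omnibus area effect has no sign, and the maps in D.6.4 and the before/during analysis in D.6.5 give other routes to direction. That limits the damage. It does not repair an effect that can vanish when areas truly differ.

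Finally, a reader might infer that the subjects the plan selects are the worst affected. D.4.1 selects on SBQ rate (10 per 20 min, or 2.5 per 5 min), not on duration, and long events drive most of the negative values.

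**Conclusion.** The concern holds in a limited form. Taken as written, D.6.4.3 rests its regional reading on an effect equal to about (w - f)A rather than A. Within the plan's own ranges this runs from +0.33A to -0.06A with no delay, and from +0.21A to -0.26A with a 5-s delay and 12-s windows. At the middle of both ranges (4 x 25 s) and that delay it is about zero.

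This rests on three assumptions: the variate is the time-point signal, the mean removed is the run mean (inferred from normalisation by run before alignment), and the delay, for which the protocol gives no value. A reader might infer that activated areas will generally appear deactivated. The figures do not support that: few or short events leave a reduced positive average, and with no delay only the 5 x 40 s corner of the table is negative. Mean removal does not affect the SBQ-IBH contrast, the time effect, onset or latency. Peak intensity is reduced but not reversed.

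**What to change.** In D.6.4.3, do not read regional activation from the brain-area main effect. For each event, compute mean post-onset minus mean pre-onset signal per area. The removed mean cancels from this. Test area differences in that change within SBQ and within IBH, then compare the two conditions. These are the area x time and area x time x condition effects, so the expectation of no interactions must be dropped. The pattern the plan predicts, uniform across areas in IBH and varying by area in SBQ, is already an interaction. D.6.4 should also state the MANOVA variate and the period over which the mean is removed.

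The cost is a change of wording on the same scans. There is a small downside: the change score keeps the sign but understates A when the response is delayed. With a 5-s delay it is 7/12 = 0.58A for 12-s windows and 3.8/8.8 = 0.43A at TR 2.2 s. In simulation, with both conditions responding, it was positive throughout: +0.16A to +0.92A at 3 s per image and +0.05A to +0.97A at 2.2 s, with the low ends at 5 x 40 s. It is also an interaction-type test rather than a main effect.
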